9.2 SAMPLE SIZE DETERMINATION

We conducted an a priori power analysis for each of the 5 outcome measures to estimate the minimum detectable difference in each given assumptions about analytic sample size, proportions of patients meeting outcome criteria, and intra-class correlations, all estimated from 2015-2016 HPMG pilot data of patients meeting categories for stage 3-4 CKD. The correlated sample of CKD patients within clinics was reduced to an equivalently sized independent patient sample by dividing the anticipated sample size by the design effect introduced by clustering within clinics [Neff pt = N / [1 + (nclus-1)ICCclin]]. For the BP control outcome, the correlated BP sample size (M=Neff pt * m outcomes per patient) was adjusted to account for clustering within patients [Neff obs = M / [1+ (mclus-1)ICCpt]]. Based on the effective sample sizes, we estimated the minimum proportion of CKD-CDS relative to UC patients meeting criteria for each outcome at 12 m that would be powered to reach statistical significance (power=.80, α 2=.05).

Table 2 summarizes for each outcome the sample size, mean and intra-class correlation calculated from HPMG pilot data; the data-informed assumptions used in the power analyses; and the minimum

detectable and clinically meaningful differences among CKD-CDS versus UC patients. Power analysis assumptions were either consistent with or more conservative than pilot estimates. For each outcome, the minimum statistically detectable difference is smaller than the clinically meaningful difference, even under these relatively conservative assumptions. For example, the H1 analysis is powered to detect increases in diagnosis rates of 5.8%-11.1% among CKD-CDS relative to UC patients, a difference that is notably smaller than the 20% increase that would represent significant clinical improvement and should be attainable with the CKD-CDS intervention.

Table 2. Summary of descriptive statistics calculated from HPMG pilot data, key power analysis assumptions, and minimum detectable difference in 12-month post-index outcomes among CKD-CDS relative to UC patients for Hypothesis 1 to 5 outcomes.							
	CKD Dx	ACEI / ARB	BP < 140/90	BP < 130/80	A1c <8	A1c <7	Neph referral
HPMG pilot data estimates							
N ^a	10175	9012	8975	8975	3191	3191	1161
M (%)	52.9	54.6	70.4	43.3	79.7	48.7	37.8
ICC _{clin}	.027	.003	.004	.004	0	.003	0.063
ICC _{pt}			.28	.26			
Power assumptions							
M (%)	50-60	50-60	70-80	40-50	75-85	40-50	30-40
ICC _{clin}	.01-.05	.001-.01	.001-.01	.001-.01	.001-.01	.001-.01	.05-.10
ICC _{pt}			.25-.35	.25-.35			
Minimum detectable and clinically meaningful differences (%)							
detectable	5.8-11.1	3.4-5.7	3.2-7.1	4.3-8.4	3.5-5.9	5.2-7.0	13.5-17.9
meaningful	20	10	10	10	10	10	20

^aestimated from number eligible in 17 HPMG clinics, prorated to 30 clinics assuming 13 similarly sized PN clinics

Pilot data from 2015-2016 primary care visits at 17 HPMG clinics found N=5766 adult patients aged 18-80 who had laboratory evidence of stage 3-4 CKD in 2015 and at least 1 post-index follow-up visit (median=5) before the end of 2016. PN primary clinics are similar in size and patient characteristics, suggesting a prorated N≈10,175 eligible CKD patients, including data from 13 additional PN clinics. We anticipate about 6% disenrollment from the medical group per year and about 2% per year to die. Very few patients switch from one clinic to another within HPMG or PN, and our algorithms accurately match over 95% of patients to a single PCP. In sum, we expect that data from a robust sample of patients with CKD will be available for testing Hypotheses 1-5. We will retrospectively retrieve the minimal necessary set of clinical information for conducting primary analyses as a limited dataset from the data repository that supports CKD-CDS operations.

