1 PROTOCOL SUMMARY

1.1 SYNOPSIS

Title:	A Technology-Driven Intervention to Improve Identification and Management of Chronic Kidney Disease in Primary Care
Study Description:	To prevent serious chronic kidney disease (CKD) complications such as end-stage renal disease and cardiovascular (CV) events, better strategies are needed to identify, treat, and refer CKD patients seen in primary care clinics. This project expands an existing and successful web-based clinical decision support (CDS) system to include key elements of CKD care and rigorously assesses the impact of this intervention on quality of CKD care for patients seen in primary care settings, including better recognition of CKD, better management of blood pressure (BP) and glucose, and timelier referral to nephrologists when appropriate.
Objectives:	(1) Improve identification of adults with CKD at primary care encounters; (2) Increase appropriate use of renoprotective antihypertensive medications, improve BP control, and improve glycemic management in patients with diabetes through personalized evidence-based treatment options; and (3) Increase collaboration and consultation with nephrologists when advisable.
Endpoints:	Primary Endpoints: for patients with antecedent estimated glomerular filtration rate (eGFR) evidence of stage 3-4 CKD, 18 months after the index visit, rates of (1)provider-diagnosed CKD (2)angiotensin converting enzyme inhibitor (ACEI)/angiotensin receptor blocker (ARB) orders (3)recommended BP control (4)recommended blood glucose control; and (5)ordering consults with nephrology for patients with eGFR laboratory evidence of stage 3b CKD and urine micro-albumin creatinine ratio (UMACR) >30 mg/g or patients with stage 4 CKD.
Study Population:	The study includes adult patients aged 18-75 years from 32 HealthPartners (HP) and Park Nicollet (PN) clinics in Minnesota. This includes adult patients at study clinics with an encounter with a primary care provider (PCP) (general internist, family physician, adult-care nurse practitioner or physician assistant) that meet the inclusion and exclusion criteria described in Section 5 below. Patients are included in the analysis for each endpoint based on care deficits identified at the index visit.

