3 OBJECTIVES AND ENDPOINTS

OBJECTIVES Impact of the intervention on:	ENDPOINTS	GUIDELINE JUSTIFICATION FOR ENDPOINTS*
Primary		
1. provider-diagnosed CKD for patients with no documented CKD diagnosis (recognition care gap)	1. Provider-diagnosed CKD in the 18-month period after an index visit	(a) Diagnostic classification of CKD based on eGFR and albuminuria category;
2. ACEI/ARB orders for patients with diagnosed hypertension or nephropathy and no current ACEI/ARB (ACEI/ARB care gap)	2. ACEI/ARB orders in the 18-month period after an index visit	(b) use of ACEIs or ARBs in adults with diabetes and UMACR 30-300 mg/g OR all patients with UMACR >300 mg/g;
3. recommended BP control for patients with consecutive elevated BP (BP care gap)	3. Recommended BP control by the end of the 18-month period after an index visit	(c) BP control to <140/90 mm Hg in adults with CKD and normal UMACR <30 mg/g OR <130/80 mm Hg in adults with ACR >300 mg/g;

OBJECTIVES Impact of the intervention on:	ENDPOINTS	GUIDELINE JUSTIFICATION FOR ENDPOINTS*
4. recommended blood glucose control for patients with elevated A1c (glucose care gap)	4. Recommended blood glucose control by the end of the 18-month period after an index visit	(d) Glycemic control using individualized A1C targets of less than 7% or less than 8% in patients with limited life expectancy, cognitive impairment, or increased risk of hypoglycemia;
5. rates of consultation with nephrology for patients with stage 4 CKD or stage 3b CKD and UMACR >30 mg/g and no recent consultation with a nephrologist (nephrology care gap)	5. Nephrology consultation in the 18-month period after an index visit	(e) Timely nephrology care
Secondary		

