4.4 END OF STUDY DEFINITION

The end date for the study is defined as the date that corresponds to 18 months after the index visit of the last person enrolled at a study clinic during the 11 month patient accrual period. Note that the accrual period was shortened from 12 to 11 months due to the onset of the Covid-19 pandemic in March 2020. The pandemic also caused disruptions in care delivery and decreased volume of primary care encounters in mid-2020 which interrupted intervention delivery during this period. We extended the follow-up period from 12 months to 18 months to increase the number of patients with primary care encounters and follow-up measures needed to assess intervention impact.

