5 STUDY POPULATION

5.1 INCLUSION CRITERIA

Clinics are the primary unit of randomization. Medical group leaders at HPMG and PN agreed to enroll at least 30 primary care clinics in this study and provided letters of support. In order to be eligible for the study, a clinic was required to meet the following requirements:

- 1) Be a HealthPartners Medical Group or Park Nicollet care system clinic
- 2) Have an established adult primary care department within the clinic (family medicine, adult medicine, and/or combined pediatrics/internal medicine)
- 3) Have a minimum of 20 study eligible patients
- 4) Have access to a nephrologist or nephrology clinic within reasonable geographic proximity

Eligible Adult Patients:

Patients with an encounter with a primary care provider (general internist, family medicine physician, advanced practice nurse or physician assistant) at a study clinic were eligible for the CKD-CDS if the following criteria were met:

- 1) Aged 18 to 75 years, inclusive on their index date. The evidence-based guidelines on which the CDS intervention is based are not applicable outside this age range.⁶²
- 2) Have laboratory evidence of CKD based on eGFR values <60 cc/min/1.73m², including the most recent eGFR value on or prior to index date, and the closest previous eGFR done at least one week prior
- 3) Have one or more CKD care components suboptimally managed at the time of the index visit.

		suboptimally managed if
CKD recognition care gap	1.1) CKD not documented in the electronic health record	1.1) ICD-10 codes N18.3, N18.4, N18.5, N18.6, N18.9 at <2 outpatient encounters, and not on the problem list, in the previous 2 years
ACEI / ARB care gap	2.1) stage 3 CKD; and 2.2a) diagnosed hypertension, or 2.2b) nephropathy; and 2.3) no evidence of hyperkalemia; and 2.4) ACEI / ARB not current at index	2.1) eGFR 30-<60 cc/min/1.72m ² ; and 2.2a) ICD-10 codes I10, I11.x, I12.x, I13.xx, I15.x, I16.x at 1 inpatient or 2 outpatient encounters, or on the problem list, in the previous 2 years, or 2.2b) UMACR >= 30 mg albumin / g creatinine ; and 2.3) no ICD-10 code E87.5 or serum potassium >= 6.5 mg / dl in the previous 2 years; and 2.4) no ACEI / ARB orders with start date before or on index date, or end date on or after index date
BP care gap	3.1) 2 consecutive elevated BP	3.1) index BP and next most recent BP >= 130/80 mm Hg

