9.3 POPULATIONS FOR ANALYSES

Individuals who meet all study wide inclusion and exclusion criteria at an index visit as described in Section 5 will be considered for inclusion in the primary analyses. Study-eligible patients will be included in the Hypothesis 1 through 5 according to the care gaps, defined in Section 5.1, that are present at the time of their index visit.

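### Table 2 sizes H1, H2, H4 and H5 on every CKD patient in each domain, but each test takes only patients with that care gap at index, so N is about 1.6 to 2.6 times too large

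*Combined protocol and SAP*

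**What the plan says.** Section 9.2 gives the power analysis for the five primary outcomes. Its H1 example is that "the H1 analysis is powered to detect increases in diagnosis rates of 5.8%-11.1% among CKD-CDS relative to UC patients", against a meaningful difference of 20. Table 2 gives N = 10,175 (CKD diagnosis), 9,012 (ACEI/ARB), 3,191 (A1c) and 1,161 (nephrology referral), and its caption describes the "minimum detectable difference in 12-month post-index outcomes among CKD-CDS relative to UC patients". The text explains that the pilot "found N=5766 adult patients aged 18-80 who had laboratory evidence of stage 3-4 CKD in 2015", prorated from 17 to 30 clinics to reach about 10,175.

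The analysis sets are defined differently:

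- Section 1.1: "Patients are included in the analysis for each endpoint based on care deficits identified at the index visit".
- Section 3, first objective: "provider-diagnosed CKD for patients with no documented CKD diagnosis (recognition care gap").
- Section 9.3: "Study-eligible patients will be included in the Hypothesis 1 through 5 according to the care gaps, defined in Section 5.1, that are present" at the index visit.

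Section 5.1 defines the gaps. They exclude patients already diagnosed, already on an ACEI or ARB, with A1c below 7, or with a nephrology visit in the prior year. The ACEI/ARB gap is also limited to stage 3. The age rule there is "Aged 18 to 75 years, inclusive on their index date". Section 4.4 records that "the accrual period was shortened from 12 to 11 months" and that follow-up was extended from 12 to 18 months.

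**The concern.** A patient who already has a CKD diagnosis, an ACEI/ARB order, A1c below 7 or a recent nephrology visit is counted in the power N but cannot enter the corresponding test. The assumed outcome rates (50-60% for H1 and H2, 40-50% for A1c<7, 30-40% for H5) are likewise prevalences in the whole domain. In the tested set everyone starts without the outcome, so the relevant rate is conversion under usual care over 18 months. Neither N nor the rate belongs to the population being tested.

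Readers will take Table 2 as what the planned tests can detect. That matters most for a null result, where the stated detectable difference would be used to judge what had been ruled out. Section 9.2 also rests its adequacy claim on detectable being smaller than meaningful for every outcome, and that comparison has not been made for the patients analysed.

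**Working it through.** **Inputs.** Section 9.2 and Table 2: power 0.80, two-sided 0.05, the design-effect formula, N, rates, ICCs and 30 clinics. Section 4.2: 1:1 allocation. Table 1: pilot shares already meeting each outcome.

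**Formulas.** Neff = N / [1 + (N/k − 1) × ICC], with k clinics and n = Neff/2 per arm. For usual-care rate p, solve for d in

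Φ{[d − 1.96·√(2p̄(1−p̄)/n)] / √[p(1−p)/n + (p+d)(1−p−d)/n]} = 0.80, where p̄ = p + d/2.

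**Step 1: reproduce Table 2.** For H1, 5,766 × 30/17 = 10,175. At ICC .01 the design effect is 1 + (10,175/30 − 1) × .01 = 4.38, so Neff = 2,322. At p = .5, d = 5.80. The same route for every outcome:

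| | N | Low corner (p, ICC) | d | High corner (p, ICC) | d | Stated |
|---|---|---|---|---|---|---|
| H1 | 10,175 | .5, .01 | 5.80 | .6, .05 | 11.15 | 5.8-11.1 |
| H2 | 9,012 | .5, .001 | 3.36 | .6, .01 | 5.70 | 3.4-5.7 |
| H4, A1c<7 | 3,191 | .5, .001 | 5.21 | .4, .01 | 7.04 | 5.2-7.0 |
| H5 | 1,161 | .3, .05 | 13.42 | .4, .10 | 17.87 | 13.5-17.9 |

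All agree within 0.1 point, so no restriction to gap patients was applied. (9,012 is 5,107 × 30/17, everyone with hypertension or ACR ≥30. The H4 and H5 counts do not prorate exactly from Table 1, where 2,066 and 636 give 3,646 and 1,122, but their means are near the whole-domain rates.)

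**Step 2: estimate the gap N.** The documents give no gap counts, so take N × (1 − Table 2 mean):

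- H1: 10,175 × .471 = 4,792; ratio 2.12.
- H2, stage 3 only, from Table 1: (3,263 × .406 + 1,470 × .431) × 30/17 = 3,456; ratio 2.61.
- H4: 3,191 × .513 = 1,637; ratio 1.95.
- H5: 1,161 × .622 = 722; ratio 1.61.

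**Step 3: recompute at the same corners.** For H1 at ICC .01 the design effect falls to 1 + (4,792/30 − 1) × .01 = 2.59, so Neff is 1,852 and d = 6.49. At ICC .05 Neff only falls from 568 to 536. Smaller clusters absorb most of the H1 loss.

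| | Gap N | Detectable, 30 clinics | 32 clinics, N × 32/30 | Power at stated difference | Power at meaningful difference |
|---|---|---|---|---|---|
| H1 | 4,792 | 6.5-11.5 | 6.3-11.1 | 71-77% | over 98% |
| H2 | 3,456 | 5.0-6.7 | 4.9-6.5 | 47-66% | over 98% |
| H4 | 1,637 | 7.1-8.5 | 6.9-8.2 | 54-64% | 91-98% |
| H5 | 722 | 14.8-18.9 | 14.3-18.3 | 73-76% | 84-97% |

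**Step 4: sensitivity to the gap share.** Taking the share from the other table changes little: H1 N 5,169, 6.4-11.4; H2 N 3,792 (9,012 × .454 × 4,733/5,107), 4.8-6.6; H4 N 1,586, 7.2-8.6; H5 N 632 (1,161 × .544), 15.2-19.2.

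**Step 5: sensitivity to the usual-care rate.** The documents give no rates for gap patients. Under *assumed* rates, with the gap N and the plan's ICCs, power at the stated differences across the four outcomes is 84-96% at 10%, 63-84% at 20% and 53-78% at 30%.

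**Step 6: H3.** Section 9.2 inflates the BP sample by several outcomes per patient, while section 9.4.1 defines one. With one outcome per patient and a gap N of 5,089 to 5,627 (8,975 × .567 and × .627), d is 4.0-6.4 against the stated 4.3-8.4 for BP <130/80. No loss of power is shown for H3, but the calculation does not match the analysis.

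**The case against.** The best defence is that the inference survives. At the plan's rates and ICCs every detectable difference remains below the meaningful one, with power there of at least 84%. H1, the example quoted, moves least. H5 is close only at its worst corner; at the pilot ICC of .063 and a 40% rate it is about 16.3 against 20. This stands, and the finding is not that the trial is underpowered.

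Second, the power losses pair a corrected N with rates that also do not belong to gap patients. This stands too. At an assumed 10% usual-care rate all four outcomes do better than stated. At 20%, H1 improves (5.5-10.5), H5 is no worse (13.5-17.0), and H2 (4.2-5.9) and H4 (6.0-7.3) remain less favourable. The direction is therefore open until gap-patient rates are supplied.

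Third, the gap counts are proxies. Table 2 means refer to 12-month outcomes and not to status at index. Table 1 uses a 2-year nephrology window where the gap uses one year, and its diabetes group admits patients by A1c alone. The ratios are approximate, but the mismatch does not depend on them.

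Fourth, section 9.1 words the hypotheses for whole domains, as Table 2 does, and the calculation is labelled a priori. But section 9.3 sets the analysis populations, sections 1.1 and 3 agree with it, and section 9.2 speaks in the present tense of what the H1 analysis is powered to detect.

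**Conclusion.** The concern holds. The stated detectable differences for H1, H2, H4 and H5 describe a population the trial will not test. N is overstated by roughly 1.6 (H5) to 2.6 (H2), as estimated from pilot shares. Holding the plan's rates and ICCs, the effect is small for H1, about one point for H5, and largest for H2 and H4, where the low end rises from 3.4 to 5.0 and from 5.2 to 7.1. Adequacy against the meaningful differences is not overturned at those rates, but it cannot be confirmed for gap patients without their usual-care rates. The ages 18-80, 30 clinics (the trial has 32) and 12-month outcomes also differ from the current design, and accrual has since been shortened. The effect of the age cap could not be quantified. This should be corrected, but it does not threaten the primary analysis.

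**What to change.** Recompute Table 2 from the pilot data for care-gap patients aged 18-75. Use gap-specific N, usual-care rates and ICCs, 32 clinics, 11-month accrual, 18-month outcomes and one binary outcome per patient, including for H3. The pilot ran only from 2015 to the end of 2016, so patients identified after mid-2015 lack 18 months of follow-up; where the 18-month rate has to be extrapolated, say so and show a range. Then restate the detectable differences, the H1 example and the sentence comparing them with the meaningful differences, and align the hypothesis wording in section 9.1 with the populations in section 9.3.

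The cost is one re-run of existing pilot data and a replaced table. No enrolment is added and the analysis model is unchanged. The detectable differences may come out less favourable than those now printed.

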9.3 POPULATIONS FOR ANALYSES

Individuals who meet all study wide inclusion and exclusion criteria at an index visit as described in Section 5 will be considered for inclusion in the primary analyses. Study-eligible patients will be included in the Hypothesis 1 through 5 according to the care gaps, defined in Section 5.1, that are present at the time of their index visit.

9.4 STATISTICAL ANALYSES

9.4.1 GENERAL APPROACH

All 5 hypotheses quantify the extent to which the CKD-CDS intervention relative to UC reduces deficits in measures of CKD care. Each will be defined as a single outcome based on data accrued in the 18 months after each patient's index visit. For all 5 measures, it is expected that the CKD-CDS intervention will positively impact the quality of care delivered to eligible patients with CKD.

9.4.2 ANALYSIS OF THE PRIMARY EFFICACY ENDPOINT(S)

9.4.2.1. Analysis plan. All hypotheses will be tested using random coefficients models in which each binary post-index outcome (e.g., recognition in 18m) will be predicted via a link function from a fixed clinic-randomized treatment group predictor, Y_{10} ; fixed clinic predictors for characteristics balanced at randomization, Y_{*0} ; a fixed pre-index outcome status where appropriate, Y_{01} ; and a random clinic intercept, V_j , such as:

$$\text{logit}(BP<130/80 18m_{ji}) = Y_{00} + Y_{10}\text{CKD-CDS}_j + Y_{*0}\text{balancing}_j + Y_{01}\text{SBP index}_i + [V_j].$$

Parameter Y_{10} is expected to be positive and statistically significant, indicating that patients in clinics randomly assigned to receive the CKD-CDS intervention are more likely to meet CKD recognition (H1), ACEI / ARB use (H2), BP control (H3), A1C control (H4) and nephrology referral (H5) thresholds in the 18 months post-index than patients in UC clinics, accounting for random variation across clinics and their own pre-index status on these outcomes.

The difference in predicted likelihoods of meeting each of the 5 outcomes through 18 months post-index will be estimated via planned contrasts and reported for ease of interpretation.

Secondary outcomes may be calculated using different thresholds (e.g., A1c<8) or treated as continuous variables (e.g., SBP in mm Hg) with adaptations made to the analysis models as necessary (e.g., identity link). Secondary analyses may include assessing (a) rates of treatment intensification among patients not at their BP or glucose goals, (b) variation in CKD treatment patterns across PCPs, (c) treatment effect heterogeneity, (d) intervention costs, (e) rate of occurrence and time to major CV events, and (e) rate of occurrence and time to hospital admissions or emergency department visits by eligible study subjects by treatment arm. We may also assess the impact of the CKD-CDS on NSAID use and medication adherence and treatment heterogeneity across demographic and racial groups.

9.4.2.2. Key Covariates. A key covariate in the H1-H5 hypothesis tests will be a binary indicator to denote whether the clinic in which the patient is seen was randomly assigned to the CKD-CDS intervention or the UC arm of the study. A second, pertinent to H3, quantifies the amount of time elapsed between the index visit and each measured BP. This covariate will be coded as (days since index/365) so that it quantifies the predicted annual change in BP control. Similarly, should the time elapsed between index and the last observed A1C differ by treatment group, log (time elapsed) may be included as an offset in the H4 analysis. Index CKD stage may be an important modifier of the CKD-CDS intervention. Stage 3-4 CKD will be defined based on the eGFR of 15-59 cc/min/1.73m² on the most recent eGFR test before the date of an index visit (stage 3a = 45-59, stage 3b = 30-44, stage 4 = 15-29), plus 1 or more antecedent eGFR values <60 cc/min/1.73m². Several other measures merit consideration as either secondary outcomes or as mediators or moderators of the primary analyses. These include (a) number of PCP patient encounters, (b) patient characteristics, including demographics and pre-intervention clinical

values and comorbidities (ICD-10 diagnosis codes and problem lists), and (c) PCP variation in baseline measures of CKD care.

9.4.2.3. Missing data. Data elements required for calculating the primary outcomes are extracted from EHR production tables. The absence of documentation of a care process, vital sign, or medication should not be interpreted as a missing value but rather as indicative of a care process or test not having been performed or medication not prescribed within the health system. Truly missing observations (eg, systolic BP measured, value not available) will be extremely rare, undetectable and assumed to be missing at random (MAR). The estimation techniques used in random coefficient models readily accommodate structural variation across observations in the amount of data present (eg, patients per clinic) and lead to unbiased parameter estimates and accurate standard errors when data are MAR.

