If this intervention is effective, it is immediately scalable and could (a) improve quality of care for large numbers of CKD patients, thereby slowing progression of CKD and improving quality of life, (b) maximize the clinical return on massive public and private investments now being made in sophisticated outpatient EHR systems, and (c) provide a health informatics prototype that rapidly and consistently translates evolving evidence-based CKD clinical guidelines into delivery of personalized and coordinated CKD care within primary care settings.

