2.3.2 KNOWN POTENTIAL BENEFITS AND THEIR ASSESSMENT

No claim is made in communications with study subjects (whether providers or patients) that any personal benefit will accrue from participating in this project.

PCPs will have no defined benefits from participating in this project. However, the decision support designed to optimize CKD care may serve to familiarize some providers with new and potentially useful information that can be used to improve the clinical care they deliver in the present or the future. No providers or patients will receive monetary compensation for any aspect of the study unless specifically recruited and consented for interviews to assess the CDS design or experience.

As documented in this proposal, there are major existing deficits in the quality of CKD care delivered in primary care clinics nationally and internationally. Improved CKD care can reasonably be expected to reduce the burden of morbidity or mortality related to progressive renal disease and major cardiovascular events. If the interventions fail to improve CKD care, this knowledge will also be important since it will direct the attention of investigators to other, potentially more fruitful lines of investigation. Thus, regardless of specific findings, the results of this trial will provide important new knowledge that will ultimately contribute to improved care for adults with CKD.

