a) Use of non-steroidal anti-inflammatory drugs (NSAIDs) b) Medication adherence c) Treatment heterogeneity d) Treatment intensification among patients not at their BP or glucose goals e) CKD treatment patterns across PCPs f) safety issues, including hypotension, hypoglycemia, and electrolyte disturbances, emergency department (ED) visits, hospital admissions for renal and non-renal causes, major CV events, and mortality as deemed necessary per the data safety and monitoring plan g) Understand provider perspective in development of the prototype of the CDS	a) Rates of NSAID use b) Medication adherence scores to blood pressure and glycemia medications c) Treatment heterogeneity d) Rates of treatment intensification among patients not at their BP or glucose goals e) Variations in CKD treatment patterns across PCPs f) safety issues, including hypotension, hypoglycemia, and electrolyte disturbances, emergency department visits, hospital admissions for renal and non-renal causes, major CV events and mortality g) Provider experience with the CKD-CDS tools based on interview data	
Rates of treatment intensification, variations of CKD care across PCPs and overall treatment heterogeneity are indicators of provider utilization of the CKD-CDS.
 
On the patient side, treatment heterogeneity and care disparities are additional measures of overall quality of care.
 
We have a data safety and monitoring plan that includes assessing safety issues like hypotension, hypoglycemia, electrolyte disturbances and ED visits among others.
 
End user experience is important for future scaling up if the intervention is successful

* The endpoints for this study correlate with strongly rated recommendations for slowing progression of CKD in multiple clinical guidelines⁵⁻⁷.

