4.1 OVERALL DESIGN

- A statement of the hypothesis: CKD is a common and serious chronic disease that often leads to end-stage renal disease and major cardiovascular events. Although evidence-based CKD care can slow

disease progression and avert complications, less than 10% of CKD patients currently receive major elements of CKD care in a timely fashion. We hypothesize that the intervention will 1) Improve identification of adults with CKD at primary care encounters; (2) Increase the appropriate use of renoprotective antihypertensive medications, improve blood pressure control, and improve glycemic management in patients with diabetes through personalized evidence-based treatment options; and (3) Increase collaboration and consultation with nephrologists.

- Phase of the trial: 3
- A description of the type/design of trial to be conducted: This study is a prospective, 2-arm, cluster randomized trial, randomizing primary care clinics at HealthPartners and Park Nicollet to intervention and usual care arms. It is a single site study.

Figure 3: Study Design

- A description of methods to be used to minimize bias: Covariate-based constrained randomization using a computer-generated allocation scheme was used to enhance balance across study arms on key factors. This method enables multiple factors to be balanced between treatment groups and can increase statistical power beyond simple randomization.
- Name of study intervention: Chronic Kidney Disease Clinical Decision Support (CKD-CDS), also known as CKD Wizard
- Name of sub-studies, if any, included in this protocol: None

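### Do five unranked primary hypotheses, with no stated family or success rule, need a multiplicity adjustment?

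*Combined protocol and SAP*

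**What the plan says.** The Synopsis (1.1) opens its list with "Primary Endpoints: for patients with antecedent estimated glomerular filtration rate (eGFR) evidence of stage 3-4 CKD, 18 months after the index visit, rates of" and then names five outcomes: CKD diagnosis, ACEI/ARB orders, BP control, glucose control and nephrology consultation. Section 3 lists the same five as primary, with no lead endpoint.

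Section 9.1 turns them into H1 to H5, each with its own population and outcome definition. Section 9.2 runs a power analysis for each outcome in turn. It seeks the smallest difference "that would be powered to reach statistical significance (power=.80, α 2=.05". Table 2 has a block headed "Minimum detectable and clinically meaningful differences", with an entry for every outcome. Section 9.3 places a patient in a given hypothesis only if the matching care gap was present at the index visit. Section 9.4.1 defines one outcome per hypothesis and expects benefit on all of them.

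Section 9.4.2.1 states that "All hypotheses will be tested using random coefficients models in which each binary post-index outcome" is predicted from treatment group, expects the treatment coefficient to be positive and significant, and commits to reporting the contrast for each of the five outcomes. It gives no significance level, testing order, alpha split or required number of successes.

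Elsewhere the wording is more general. Section 4.1 says "We hypothesize that the intervention will 1) Improve identification of adults with CKD at primary care encounters" and continues with two further aims. Sections 2.1, 2.3.2 and 3 speak of the intervention as a whole: "If this intervention is effective, it is immediately scalable", "If the interventions fail to improve CKD care, this knowledge will also be important" and "End user experience is important for future scaling up if the intervention is successful".

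**The concern.** Five primary tests at .05 with no stated rule is a familiar warning sign. Some sentences speak of one verdict on the intervention and link scale-up to it, yet nothing says how five results become one verdict. With mixed results, a team could decide afterwards whether one, two or all five successes mean that the intervention works. An any-one rule would raise the chance of a false overall claim well above that of one test. An all-five rule would not, but it would cut the power of the overall verdict. The level of .05 also appears only in the power section and is not repeated with the analysis.

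**Working it through.** **1. The level in use.** Section 9.2 gives Neff = N / [1 + (n per clinic − 1) × ICC]. For H1, Table 2 has N = 10,175 over 30 clinics, so n per clinic is 339.2.

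- ICC .01, usual-care rate 50%: design effect 1 + 338.2 × .01 = 4.38 and Neff = 2,322. The pooled two-proportion formula at two-sided .05 and 80% power gives 5.8 points.
- ICC .05, rate 60%: design effect 17.91, Neff = 568, giving 11.1 points.

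The plan states 5.8 to 11.1. One-sided .05 gives 5.15 at the lower end and does not fit. For H5 the same steps give 13.4 to 17.9 (stated 13.5 to 17.9). Each test is therefore two-sided at .05, or .025 in the benefit direction. The two BP columns could not be reproduced, because the number of readings per patient is not given.

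**2. The any-one reading.** All five nulls are taken as true, and only false benefit is counted. For independent tests this is 1 − .975⁵ = .119. For a common correlation ρ between test statistics it is 1 − ∫ Φ((1.96 − √ρ·u)/√(1−ρ))⁵ φ(u) du. The documents give no correlation, so ρ is an assumption.

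| ρ | chance of at least one false benefit |
|---|---|
| 0 | 11.9% |
| .3 | 10.5% |
| .5 | 9.1% |
| .8 | 6.4% |

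**3. The other readings.**

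| Reading | False benefit, ρ = 0 | ρ = .5 | Power of the verdict if each test has 80%, ρ = 0 / .5 |
|---|---|---|---|
| Five separate claims | 2.5% each | 2.5% each | 80% each |
| At least two | 0.6% | 2.4% | not computed |
| All five | below 0.1% | below 0.1% | .8⁵ = 33% / 51% |
| Any one | 11.9% | 9.1% | 99.97% / 97.6% |

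Of these, only the any-one reading puts the chance of a false overall claim above 2.5%.

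**4. What adjustment would cost.** Holm's first step across five tests uses .05/5 = .01. A test with 80% power at .05 then has Φ(2.802 − 2.576) = Φ(.226) = 59%.

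For H5 at its meaningful difference of 20 points, the pilot values (N 1,161, ICC .063, rate 37.8%) give 88% power at .01. That sample is all patients eligible for nephrology care, whereas Section 9.3 keeps only those with the gap. Table 1 shows 45.6% with a consultation within two years. If the other 54.4% remain, N = .544 × 1,161 = 632 and Neff = 632 / [1 + (21.07 − 1) × .063] = 279. Power at .01 falls to 78%, against 92% at .05. Over Table 2's ranges of ICC and rate, power at .01 is 63% to 86%. The share is approximate, because the gap definition looks back one year and Table 1 two, and rate and ICC are held unchanged.

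**The case for a change.** The strongest case for acting is that the plan never says that the five claims are separate, while it does use the language of a single verdict. Section 10.1.2 even lists the primary endpoint having been met, in the singular, as a possible ground for suspending or ending the study. Full reporting prevents selective reporting but does not stop a team from choosing the verdict rule after seeing mixed results. Mixed results are plausible, since detectable differences run from 3.4–5.7 points for ACEI/ARB to 13.5–17.9 for nephrology. One or two sentences would settle the matter at almost no cost.

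It stands that the sentence is missing, and that the any-one arithmetic is right on its own condition. The inference that the plan leaves an error rate uncontrolled does not stand. The whole-intervention sentences are rationale: one about scalability, one about the value of a null result, one about why user interviews matter. None is tied to H1–H5. The three parts in Section 4.1 are the three objectives of the Synopsis, and a list joined by "and" is not a success rule. Section 10.1.2 has no test behind it, because Section 9.4.6 plans no interim analysis. The only statements about the results jointly, in 9.4.1 and 9.4.2.1, expect benefit on all five, which is the opposite of an any-one rule. As for the level, 9.2 ties statistical significance to .05 for these same outcomes, and nothing in 9.4.2 suggests another.

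**Conclusion.** No change is needed. Followed as written, the plan yields five separately defined, powered and tested contrasts, all reported. As separate claims, each keeps its two-sided .05 and there is no inflation. A statement to that effect would record the existing structure and alter no model, test or estimate. Analysts would fill this gap in the same way without it.

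The 6% to 12% chance of a false overall claim arises only under a rule that the plan does not contain, with all five nulls true and an assumed correlation between .8 and 0. The alternatives (Holm, a lead endpoint, a minimum count, all five) are trade-offs with real costs. Holm's first step takes 80% power to 59% at the detectable difference, and H5 to roughly 78% at its meaningful difference if the care-gap subset is about 632 patients. Readers who want a family-wise view can compare the five reported results with a stricter level themselves. The conclusion assumes that the report presents all five results together, as Section 9.4.2.1 commits, and does not offer one success among five as proof that the intervention works overall.
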